## **9.3 APPENDIX 3: STUDY GOVERNANCE**

### **9.3.1 Data Quality Assurance**

This study will be conducted using the quality processes described in applicable procedural documents. The quality management approach to be implemented will be documented and will comply with current ICH guidance on quality and risk management. All aspects of the study will be monitored for compliance with applicable government regulatory requirements, current Good Clinical Practice, the protocol, and standard operating procedures (SOPs). The monitor will maintain current personal knowledge of the study through observation, review of study records and source documentation, and discussion of the conduct of the study with the investigator and staff. Electronic CRFs and electronic data capture will be utilized. The electronic data capture system is validated and compliant with US Title 21 CFR Part 11. Each person involved with the study will have an individual identification code and password that allows for record traceability. There may be an internal quality review audit of the data and additional reviews by the clinical monitor.

Steps to be taken to ensure the accuracy and reliability of data include, but are not limited to: selection of qualified investigator and appropriate study center, protocol training and review of protocol procedures with the investigator and study site personnel before the start of the study, site initiation and periodic interim monitoring visits by SIGA or PPD, and direct transmission of safety laboratory data into the PPD study database for all clinical safety laboratory tests performed. The eCRF will be reviewed for accuracy and completeness by PPD Clinical research associate (CRA) remotely and during on-site monitoring visits. Discrepancies will be resolved with the investigator or designees, as appropriate. The data will be entered into the clinical study database and validated for accuracy. During on-site monitoring visits, 100% of the data will be verified using source documentation. SIGA or Biomedical Advanced Research and Development Authority representatives may accompany the PPD CRA on any scheduled site visit. The investigator will be informed in advance of any visitors to the study site in addition to the PPD CRA.

Representatives of SIGA's Quality Assurance department (or designee) may visit the site to carry out an audit of the study in compliance with regulatory guidelines and PPD policy. Such audits will require access to all study records, including source documents, for inspection and source document verification with the eCRF. Subject privacy must, however, be respected. Sufficient prior notice will be provided to allow the investigator to prepare properly for the audit. Similar auditing procedures may also be conducted by any regulatory body reviewing the results of this study in support of a Licensing Application. The

investigator will immediately notify SIGA if they are contacted by a regulatory agency requesting a site inspection.

### **9.3.2 Investigator Obligations**

The following administrative items are meant to guide the investigator in the conduct of the study and may be subject to change based on industry and government SOPs, working practice documents, or guidelines. Changes will be reported to the IRB but will not result in protocol amendments.

#### **9.3.2.1 Confidentiality**

All laboratory specimens, evaluation forms, reports, and other records will be identified in a manner designed to maintain subject confidentiality. All records will be kept in a secure storage area with limited access. Subjects will not be identified by name in any reports in this study. All records will be kept confidential to the extent provided by federal, state, and local law. Medical records are made available for review when required by the FDA or other authorized users only under the guidelines set by the Federal Privacy Act. Direct access, as defined in the Federal Privacy Act, includes examining, analyzing, verifying, and reproducing any records and reports that are important to the evaluation of the study. The investigator is obligated to inform the subjects that these representatives may review their study-related records without violating the confidentiality of the subjects. The requirement to maintain subject confidentiality is included in the study informed consent document.

The investigator and all employees and coworkers involved with this study may not disclose or use for any purpose other than performance of the study, any data, record, or other unpublished, confidential information disclosed to those individuals for the purpose of the study. Prior written agreement from SIGA or its designee must be obtained for the disclosure of any said confidential information to other parties.

#### **9.3.2.2 Institutional Review**

Federal regulations and ICH guidelines require that approval be obtained from an IRB before participation of human subjects in research studies. Before study onset, the protocol, ICF, advertisements to be used for the recruitment of study subjects, and any other written information regarding this study to be provided to the subject or the subject's legal guardian must be approved by the IRB. Documentation of all IRB approvals and of the IRB

compliance with the ICH harmonised tripartite guideline E6(R2): Good Clinical Practice will be maintained by the site and will be available for review by SIGA or its designee.

All IRB approvals should be signed by the IRB chairman or designee and must identify the IRB name and address, the clinical protocol by title or protocol number or both, and the date approval or a favorable opinion was granted.

### **9.3.2.3 Subject Consent**

Written documentation of informed consent in compliance with US Title 21 CFR Part 50 shall be obtained from each subject before any study-related procedures are performed and study drug is administered. If any institution-specific modifications to study-related procedures are proposed or made by the site, the consent should be reviewed by SIGA or its designee or both before IRB submission. Once reviewed, the investigator will submit the ICF to the IRB for review and approval before the start of the study. If the ICF is revised during the course of the study, all active participating subjects must sign the revised ICF.

Before recruitment and enrollment, each prospective subject or his/her legal guardian will be given a full explanation of the study and will be asked to read and review the approved ICF. Once the investigator is assured that the subject/legal guardian understands the implications of participating in the study, the subject/legal guardian will be asked to give his or her consent to participate in the study by signing the ICF. A copy of the ICF will be provided to the subject/legal guardian.

### **9.3.2.4 Exclusion of Children**

Effort will be made to include women and minorities in proportions similar to that of the community from which they are recruited. Because this study is designed to establish safety of the study drug in adults, enrollment will be limited to persons at least 18 years of age, and no older than 50 years. Children are excluded from participation in this clinical study because it does not meet the Department of Health and Human Services' guidelines (45 CFR 46, Subpart D, 401-409) for inclusion of children in research. These guidelines provide guidance for the protection of children in research. Generally, healthy children can be studied when the research is considered as "not greater than minimal risk." Children can be involved in research with greater than minimal risk only when it presents the prospect of direct benefit to the individual child or is likely to yield generalizable knowledge about the child's disorder or condition.

### **9.3.2.5 Study Reporting Requirements**

By participating in this study, the investigator agrees to submit reports of SAEs according to the time line and method outlined in this protocol. In addition, the investigator agrees to submit annual reports to his or her IRB as appropriate.

### **9.3.2.6 Financial Disclosure and Obligations**

The investigator is required to provide financial disclosure information to allow SIGA to submit the complete and accurate certification or disclosure statements required under US Title 21 CFR Part 54. In addition, the investigator must provide to SIGA a commitment to promptly update this information if any relevant changes occur during the course of the investigation and for 1 year following the completion of the study.

Neither SIGA nor PPD is financially responsible for further testing or treatment of any medical condition that may be detected during the screening process. In addition, in the absence of specific arrangements, neither SIGA nor PPD is financially responsible for further treatment of the disease under study.

### **9.3.2.7 Investigator Documentation**

Prior to beginning the study, the investigator will be asked to comply with ICH E6(R2) Section 8.2 and US Title 21 of the CFR by providing essential documents, including but not limited to, the following:

- IRB approval.
- An original investigator-signed investigator agreement page of the protocol.
- Form FDA 1572, fully executed, and all updates on a new fully executed Form FDA 1572.
- Curriculum vitae for the principal investigator and each subinvestigator listed on Form FDA 1572. Current licensure must be noted on the curriculum vitae. Curriculum vitae will be signed and dated by the principal investigators and subinvestigators at study start-up, indicating that they are accurate and current.
- Financial disclosure information to allow SIGA to submit complete and accurate certification or disclosure statements required under US Title 21 CFR Part 54. In addition, the investigators must provide to SIGA a commitment to promptly update this

information if any relevant changes occur during the course of the investigation and for 1 year after the completion of the study.

- An IRB-approved ICF, samples of site advertisements for recruitment for this study, and any other written information about this study that is to be provided to the subject or legal guardians.
- Laboratory certifications and reference ranges for any local laboratories used by the site, in accordance with US Title 42 CFR Part 493.

### **9.3.2.8 Study Conduct**

The investigator agrees to perform all aspects of this study in accordance with the ethical principles that have their origin in the Declaration of Helsinki, ICH E6(R2): Good Clinical Practice; the protocol; and all national, state, and local laws or regulations.

### **9.3.2.9 Case Report Forms and Source Documents**

Site personnel will maintain source documentation, enter subject data into the eCRF as accurately as possible, and will rapidly respond to any reported discrepancies.

Electronic CRFs and electronic data capture will be utilized. The electronic data capture system is validated and compliant with US Title 21 CFR Part 11. Each person involved with the study will have an individual identification code and password that allows for record traceability. Thus, the system, and any subsequent investigative reviews, can identify coordinators, investigators, and individuals who have entered or modified records, as well as the time and date of any modifications. There may be an internal quality review audit of the data and additional reviews by PPD's CRA.

Each eCRF is presented as an electronic copy, allowing data entry by site personnel, who can add and edit data, add new subjects, identify and resolve discrepancies, and view records. This system provides immediate direct data transfer to the database, as well as immediate detection of discrepancies, enabling site coordinators to resolve and manage discrepancies in a timely manner.

Paper copies of the eCRFs and other database reports may be printed and signed by the investigator. This system provides site personnel, PPD CRAs, and reviewers with access to hardcopy audits, discrepancy reviews, and investigator comment information.

### **9.3.2.10 Adherence to Protocol**

The investigator agrees to conduct the study as outlined in this protocol, in accordance with ICH E6(R2) and all applicable guidelines and regulations.

### **9.3.2.11 Reporting Adverse Events**

By participating in this study, the investigator agrees to submit reports of SAEs according to the timeline and method outlined in this protocol. In addition, the investigator agrees to submit annual reports to his or her IRB as appropriate. The investigator also agrees to provide SIGA with an adequate report, if applicable, shortly after completion of the investigator's participation in the study.

### **9.3.2.12 Investigator's Final Report**

Upon completion of the study, the investigator, where applicable, should inform the institution; the investigator/institution should provide the IRB with a summary of the study's outcome and SIGA and regulatory authorities with any reports required.

### **9.3.2.13 Records Retention**

Essential documents should be retained until at least 2 years after the last approval of a marketing application in an ICH region and until there are no pending or contemplated marketing applications in an ICH region or until at least 2 years have elapsed since the formal discontinuation of clinical development of the study drug. These documents should be retained for a longer period, however, if required by applicable regulatory requirements or by an agreement with SIGA. SIGA is responsible for informing the investigator/institution when these documents no longer need to be retained.

### **9.3.2.14 Publications**

All information concerning TPOXX, SIGA operations, patent application, formulas, manufacturing processes, basic scientific data, and formula information, supplied by SIGA to the investigator and not previously published, is considered confidential and remains the sole property of SIGA. The investigator agrees to use this information only to accomplish this study and will not use it for other purposes without SIGA's written consent. The investigator understands that the information developed in the clinical study will be used by SIGA, in connection with the continued development of TPOXX, and thus may be disclosed as required to other clinical investigators or government regulatory agencies. To permit the

information derived from the clinical studies to be used, the investigator is obligated to provide SIGA with all data obtained in the study. Any publication or other public presentation of results from this study, including manuscripts and materials for presentation at scientific meetings, should be provided to SIGA at least 30 working days before abstract or other relevant submission deadlines. Authorship of publications resulting from this study will be determined at the discretion of SIGA.

### **9.3.3 Study Management**

#### **9.3.3.1 Monitoring**

##### **9.3.3.1.1 Monitoring of the Study**

Site monitoring for safety is conducted to ensure that human subject protection, study procedures, and laboratory, study drug dosing, and data collection processes are of high quality and meet SIGA, GCP/ICH, and regulatory guidelines. PPD CRA(s) will conduct site monitoring visits as detailed in the monitoring plan.

Site investigators will allow the CRA(s), the designated IRB, SIGA or its designee and the FDA to review, audit, and inspect study documents (eg, ICFs, drug accountability and distribution forms, eCRF), pertinent hospital and site records, and source documentation for verification of the study data.

Clinical research associates will conduct site visits in accordance with PPD SOPs to monitor the following: study operations, the quality of data collected in the research records, the accuracy and timeliness of data entered in the database, and to determine that all process and regulatory requirements are met. Study monitoring visits will occur at initiation of the study site, at intervals determined by SIGA during conduct of the study, and at completion of the study.

The CRA will maintain current personal knowledge of the study through observation, review of study records and source documentation, and discussion of the conduct of the study with the investigator and staff. During the routine monitoring visits, the CRA will perform a 100% source document verification of all subject data entered into the eCRF. Discrepancies, if any, will be clarified with the study site coordinator and investigator, and corrected at the site by the study coordinator. Any questions or required data clarifications will be sent to the study site electronically.

### **9.3.4 Safety Monitoring Plan**

Close cooperation between the designated members of the study team will occur to evaluate and respond to individual AEs in a timely manner. Designated team members (investigator, subinvestigators, study coordinator, and other designated study clinicians) will review the subject safety information and data (laboratory test results, ECGs, AEs, and concomitant medications) and update the PPD project team and the ISM on the status of all enrolled subjects at their site on a weekly basis (or more frequently if required because of an unexpected safety issue) through completion of each subject's final study visit.

### **9.3.5 Medical Monitor**

The medical monitor, or their qualified designee, will receive reports within 24 hours of study site awareness of all SAEs and within 7 days of study site awareness of all other AEs. The safety monitors will review all safety data and alert the medical monitor of SAEs and AEs of interest. The medical monitor may make a request for data to the investigator as necessary for safety evaluations.

The medical monitor will review each significant AE in a timely fashion and ensure that appropriate management is initiated and completed. Drug safety representatives and the medical monitor will have direct contact with the investigators and follow all significant events as needed.

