### **3.4.3 Halting Rules**

The medical monitor, investigator, SIGA, and ISM will review all AEs. All AEs determined by the investigator to be severe and possibly, probably, or definitely related to study drug, as well as all clinical assessments, laboratory test results, ECG results, or vital sign measurements that meet Grade 3 criteria on the DAIDS AE Grading Table will be assessed by the medical monitor, who will make a recommendation as to whether or not halting of the study should occur. At the discretion of the medical monitor, depending on the assessment of the severity of the event, the recommendation to halt the study may be made after consultation with the investigator, SIGA, and the ISM.

The study will be temporarily halted (no new enrollments and no further study drug administration) by the investigator and the medical monitor, SIGA, and the ISM will be promptly notified according to the following criteria:

- One subject experiences a Grade 4 AE assessed as possibly, probably, or definitely related to study drug.

- There is a subject death assessed as possibly, probably, or definitely related to study drug.
- One subject experiences a seizure assessed as possibly, probably, or definitely related to study drug.
- Two or more subjects experience the same or similar SAEs that are possibly, probably, or definitely related to the study drug.
- Three or more subjects experience the same or similar AEs that are Grade 3 or above and are possibly, probably, or definitely related to the study drug.

Study enrollment and study drug administration would resume if review of the AEs that caused the halt resulted in a recommendation to permit further continuation. In such an instance, SIGA, with participation by the investigator and the medical monitor, would consult with the ISM to conduct the review of all AEs that meet the criteria for halting the study. The study would remain suspended until the events were reviewed by the ISM and a recommendation was made as to whether the study should be continued or stopped. This constitutes a minimum criterion, and the decision to halt the study may be made based on any other criteria that, in the judgment of the investigator, with agreement of the medical monitor and ISM, indicate a potentially serious safety concern. The investigator will advise SIGA immediately if any of the halting rules are met.

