### **6.2.1 Adverse Events**

#### **6.2.1.1 Adverse Event Definitions**

The investigator is responsible for reporting all AEs that are observed or reported during the study, regardless of their relationship to study drug or clinical significance. If there is any doubt as to whether a clinical observation is an AE, the event should be reported.

An AE is any event or other untoward medical occurrence, including those AEs that result from dosing errors, which may present during administration of a study drug or during a reasonable follow-up period and which does not necessarily have a causal relationship with this treatment. An AE is any unfavorable and unintended sign (eg, a clinically significant

abnormal laboratory finding), symptom, or disease temporally associated with the use of a medicinal product, whether or not considered to be related to the medicinal product. All AEs will be followed until the AE is resolved or stabilized as determined by the investigator and/or the medical monitor.

A treatment-emergent AE (TEAE) is defined as any event not present before exposure to study drug or any event already present that worsens in intensity or frequency after exposure to study drug.

An adverse reaction is any AE caused by a drug. Adverse reactions are a subset of all suspected adverse reactions for which there are reasons to conclude that the drug caused the event.

A suspected adverse reaction is any AE for which there is a reasonable possibility that the study drug caused the AE. For the purposes of IND safety reporting, “reasonable possibility” means that there is evidence to suggest a causal relationship between the drug and the AE. A suspected adverse reaction implies a lesser degree of certainty about causality than adverse reaction, which means any AE caused by a study drug.

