### **6.2.1.4 Reporting of Serious Adverse Events**

Any AE considered serious by the investigator or which meets SAE criteria (Section 6.2.1.1), or any other event or condition regardless of grade, which in their judgment represents a reportable event, must be reported to the medical monitor and SIGA as soon as the investigator becomes aware of the event. In addition, the event must be reported to PPD via the SAE hotline. The PPD SAE Report Form must be submitted within 24 hours of knowledge of the event. SIGA (or designee) will be responsible for notifying the relevant regulatory authorities of any SAE as outlined in US Title 21 Code of Federal Regulations (CFR) Parts 312 and 320. The investigator is responsible for notifying the institutional review board (IRB) directly.

In addition, the investigator (or designee) must report any Grade 3 (severe) AE that they deem possibly, probably, or definitely related to study drug to the medical monitor and SIGA within 24 hours after becoming aware of the event.

After notification from the investigator, SIGA will report all study drug-related and unexpected SAEs (those not listed in the TPOXX full prescribing information) to the FDA within 15 calendar days of first knowledge. Fatalities or life-threatening events assessed as related and unexpected will be reported to the FDA within 7 calendar days of first knowledge. The ISM will also receive these reports.

The following contact information is to be used for SAE reporting:

[REDACTED]

The collection and monitoring period for SAEs is 30 days after administration of the last dose of study drug. At the time of discharge or early termination from the study site, the subject will be instructed to notify the investigator of any SAEs that occur within 30 days after the last dose of study drug.

All subjects will have a follow-up telephone call 30 days after administration of the last dose of study drug (Day 37 [+2 days]) to report any SAEs.

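### For a non-serious Grade 3 finding judged unrelated, the only fixed limit for reaching the medical monitor, who must advise on halting, is 7 days

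*Protocol*

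**What the plan says.** Three sections of the protocol bear on when the medical monitor learns of a Grade 3 event.

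- **3.4.3 Halting Rules** gives the medical monitor two classes to assess. One is severe AEs that the investigator considers related. The other is "all clinical assessments, laboratory test results, ECG results, or vital sign measurements that meet Grade 3 criteria on the DAIDS AE Grading Table", with no condition on relatedness. Both "will be assessed by the medical monitor, who will make a recommendation as to whether or not halting of the study should occur". A halt stops new enrolment and further dosing.
- **6.2.1.4 Reporting of Serious Adverse Events** adds a rule for some non-serious events, with a limit of 24 hours from awareness. The investigator "must report any Grade 3 (severe) AE that they deem possibly, probably, or definitely related to study drug to the medical monitor and SIGA".
- **9.3.5 Medical Monitor** sets the general limits: the monitor receives reports "within 24 hours of study site awareness of all SAEs and within 7 days of study site awareness of all other AEs". It makes no exception by grade.

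**The concern.** The halting section and the reporting sections draw their lines in different places. Section 3.4.3 sends Grade 3 results to the medical monitor regardless of causality. The short reporting limit depends on the investigator's view of causality. A non-serious Grade 3 AE that the site judges unlikely or not related is therefore one on which the monitor must advise, yet its only fixed limit is 7 days, as long as the whole dosing period.

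What is at stake is the study-level review. Each specific event listed in 3.4.3 as a mandatory halt requires a related event, so for findings called unrelated the review route named there is the medical monitor's recommendation. Part of its value is a second look at a single site's causality judgment in an open-label study. Letting that same judgment decide which limit applies weakens the check. A late recommendation bears on other subjects being dosed or about to start, as well as on the subject with the finding.

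**Working it through.** **Step 1: which fixed limit applies to which class**

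| Class | Fixed limit to the medical monitor | Source |
|---|---|---|
| SAE | 24 h | 9.3.5 |
| Non-serious Grade 3 AE, possibly, probably or definitely related | 24 h | 6.2.1.4 |
| Event meeting a listed mandatory halt | Prompt notice with the halt | 3.4.3 |
| Non-serious Grade 3 AE, unlikely or not related | 7 days | 9.3.5 |
| Grade 3 result not recorded as an AE | None stated | – |

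The last row should seldom arise, because 6.2.1.1 says: "If there is any doubt as to whether a clinical observation is an AE, the event should be reported". The fourth row is the gap.

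**Step 2: the limit against one subject's dosing**

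Inputs: twice-daily dosing on Days 1 to 7, intervals of 12 h ± 30 min (5.1); AEs assessed from the first dose (6.2); limit 7 days (9.3.5).

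- Doses: 2 × 7 = 14, so 13 intervals. Nominal last dose: 13 × 12 = 156 h after the first.
- Limit: 7 × 24 = 168 h after awareness. Awareness cannot precede the first dose, so the limit expires at 168 h or later.
- Nominal margin: 168 − 156 = 12 h or more after the last dose.
- Every interval at its longest: 156 + 13 × 0.5 = 162.5 h; margin 168 − 162.5 = 5.5 h or more.

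The limit thus expires after that subject's last dose whenever the finding is made during treatment.

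**Step 3: 7 days against 24 hours**

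- Difference: 168 − 24 = 144 h.
- Another subject in treatment: 144 / 12 = 12 further doses at most.
- The affected subject, with the site aware at the 4-hour ECG (6.2.5) and nominal dose times:

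| ECG | Awareness | Further doses by 7-day limit | Further doses by 24-hour limit | Difference |
|---|---|---|---|---|
| Day 1 | 4 h | 13 (by 172 h) | 2 (by 28 h) | 11 |
| Day 4 | 76 h | 7 (by 244 h) | 2 (by 100 h) | 5 |
| Day 7 | 148 h | 1 | 1 | 0 |

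The number of new subjects who could start in those 144 hours cannot be computed, because the protocol gives no enrolment pace. All these counts assume that the report waits for the full limit and that dosing continues meanwhile.

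**The case against.** The best defence is that 7 days is a ceiling and that several faster routes exist.

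- Section 6.2.1.4 also tells the investigator to report to the medical monitor and the sponsor, as soon as aware, any event of any grade that the investigator considers reportable.
- In 9.3.5 the safety monitors review all safety data and alert the medical monitor to AEs of interest. The medical monitor has direct contact with investigators and "will review each significant AE in a timely fashion and ensure that appropriate management is initiated and completed".
- Section 6.2.1.3 names the medical monitor among those reviewing AE data on an ongoing basis.
- Section 9.3.1 provides for "direct transmission of safety laboratory data into the PPD study database for all clinical safety laboratory tests performed".
- Section 3.4.3 lets the investigator, with the agreement of the medical monitor and the independent safety monitor (ISM), halt on criteria beyond those listed.
- Section 3.4.1 lets the investigator withdraw a subject for a Grade 3 or 4 event, and subjects stay on site until Day 9.

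All of this stands and lowers the risk. But each route depends on judgment, carries no time limit, or does not fix when the medical monitor is told. The direct data transfer names laboratory tests only, not ECGs or vital signs. The weekly update in 9.3.4 goes to the contractor's project team and the ISM. The Safety and Medical Management Plan named in 9.3.6 is not shown and may set tighter times, but the protocol's own figure would still be 7 days.

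A reader might infer more than the text supports:

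- **That 9.3.5 and 6.2.1.4 contradict each other on related Grade 3 AEs.** They do not: a report within 24 hours satisfies both. Only a cross-reference is missing.
- **That mandatory halts could be delayed.** Each listed event must be related, and the investigator halts the study with prompt notice.
- **That the affected subject goes on being dosed unprotected.** The on-site investigator can withdraw that subject without waiting for the medical monitor.
- **That values worse than Grade 3 escape review because the sentence in 3.4.3 names only Grade 3.** That reading is strained; at most the wording could be clearer.

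**Conclusion.** The gap is real and narrow. It concerns non-serious Grade 3 AEs judged unlikely or not related that the investigator does not otherwise choose to report at once. For these, the protocol asks for a halting recommendation but guarantees notice to the person making it only within a period that outlasts the subject's dosing. Lateness is possible, not certain, and the doses in the working are upper bounds.

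Only the discretionary recommendation can be late. SAEs, related Grade 3 AEs and the listed mandatory halts are unaffected. Severity is low to moderate. The case for change is that it costs almost nothing. With a 24-hour limit, a Day 1 finding would reach the medical monitor by Day 2 and a Day 4 finding by Day 5, both before the last dose; the present limits fall on Day 8 and Day 11.

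**What to change.** In 9.3.5, require that SAEs, all AEs of Grade 3 or above, and all findings that 3.4.3 refers for review (whether or not recorded as AEs) reach the medical monitor within 24 hours of site awareness, regardless of causality. Limit the 7-day deadline to non-serious AEs of Grade 1 or 2. Align 6.2.1.4 with this and cross-refer between the two sections. While editing, the review sentence in 3.4.3 can also say Grade 3 or above, as a clarification.

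The change is to protocol wording, with the safety plan aligned to match. The downside is a few more expedited reports from the single site.
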